15.2 Exclusion criteria

General

1. Lack of written informed consent.
2. Women with the possibility of having children, without using contraception (oral contraceptive pill, intrauterine contraceptive device, contraceptive implant, patch or condom).
3. Pregnant women or breastfeeding.
4. Subjects that can not be assessed partially or totally according to the protocol.
5. Subjects with topical, systemic or intravenous medication with any type of antibiotic on the day of the baseline visit.
6. Subjects with topical, systemic or intravenous medication with any type of medication that interferes decisively with the results of the study.
7. Subjects with a history of hypersensitivity to any of the components of the formula of the research product or its analogues.
8. Positive substance abuse (smoking, alcoholism, marijuana). *
9. Subjects who have participated in any clinical research study in the last 40 days, prior to inclusion in the study.
10. Subjects legally or mentally incapacitated to give their consent to participate in this study.
11. Any clinically important abnormalities detected during the clinical examination, tests that could interfere with the conduct of the study or with the evaluations of efficacy and safety.

* Repeated consumption of one or several psychoactive substances, to the point that the consumer (known as an addict) becomes intoxicated periodically or continuously, shows a compulsive desire to consume the preferred substance (or substances), has an enormous difficulty interrupting voluntarily or modify the consumption of the substance and is determined to obtain it in any way. -Definition of WHO *

Related to ophthalmological criteria

1. Eye surgery in the past 6 weeks.
2. Active ulcerative keratitis.
3. Recurrent corneal erosion syndrome.
4. Suspected viral or allergic conjunctivitis.

Related to a therapy or previous and / or concomitant treatments

Current therapy or expected therapy with:

Systemic NSAIDs, corticosteroids, antihistamines or immunosuppressants.

Typically, patients can not be treated at the baseline visit with any other type of antibiotic topical ophthalmic, as well as steroids, NSAIDs, mast cell stabilizers, antihistamines, decongestants. If the patients prior to this day were under treatment with another antibiotic or drugs of those mentioned may be included.

To know the other prohibited treatments and their rest period, please refer to Table 4 "Main prohibited treatments"

Elimination Criteria

- Any complication or lack of control that the doctor considers should be treated differently.

- **Elimination Criteria**

- Clinicians:

a. Any complication or lack of control that the doctor considers should be treated differently. The following points should be considered:

i. The no improvement of the initial clinical signs and symptoms.

ii. Diagnosis added or different to that of acute bacterial conjunctivitis.

iii. Use other medications outside the study.

b. * It is reiterated that they are minimum parameters to be considered, any other case in which the investigator considers necessary the elimination of the patient and suspension of the treatment must be informed and evaluated by the sponsor.

- For the sponsor:

- a. By its will, it will not have penalties, nor will it lose benefits to those that it already has right.
- b. For the total term of the scheduled visits in the clinical study.
- c. For a serious adverse event related to the medication that endangers your health.
- d. Why the medication does not work at the doctor's discretion.

and. Why, by sponsor's decision, the study ends earlier.

In case of withdrawal for any of these reasons or any other at the discretion of your doctor, you will be prescribed again the medication of which you were already a user or any other that is of benefit for your best treatment.

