4 INFORMATION ABOUT BACKGROUND

4.1 INTRODUCTION

Conjunctivitis (partial or total inflammation of the conjunctiva) caused by an external pathogen can be divided into bacterial and viral, however we must not forget that if we take into account its etiology we can name by fungal, allergic, autoimmune and by physical means (heat burns, friction, chemical).

In the following document, we will concentrate on exposing the epidemiological and clinical panorama of conjunctivitis caused by pathogens (bacteria and viruses) and the suffering related to the mass.

Currently about 6 million cases are registered per year in the general consultation (1% of the total annual consultations), this does not mean that all cases will be sent to the ophthalmologist, however as a reason for consultation 70% of the subjects come first with a family doctor and 35% refer to ophthalmologists because it is a case that does not remit with symptomatic or because the severity warrants it.

The cost of treating conjunctivitis according to data collected in the American union represents more than 377 million dollars a year.

Viral conjunctivitis:

Viral conjunctivitis represents an average of 80% of reported cases, it is estimated that 50% of these will be misdiagnosed as bacterial, this when compared to positive cultures.

65-90% of cases are caused by adenoviruses found in any of its two pathogenic entities, either in the form of epidemic keratoconjunctivitis or pharyngo-conjunctival fever. Clinically both are characterized by local inflammatory reactions, hyaline secretion, chemosis, photophobia, hyperemia, corneal deposits and lymphadenopathy.

The adenovirus is highly contagious and an estimated 10 to 50% chance of spread. 46% of the cultures in the hands of patients diagnosed with keratoconjunctivitis are positive, so their spread is verified mainly by contact and fomites.

Its incubation period ranges from 5 to 12 days and its transmission period of 10-14 days.

Its treatment consists of treating the symptoms with eye lubricants, NSAIDs, eye antihistamines, cold compresses, etc. Prophylaxis with antibiotics is not indicated since its benefit has not been proven, more if complications and delay in diagnosis of other entities are reported.

Bacterial conjunctivitis:

Its incidence is estimated at 135 per 10,000 inhabitants. The main routes of infection are by contact, although the proliferation of normal flora can occur as sole etiology or concomitantly.

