The pathogenesis usually involves the disruption of the ocular surface defense mechanisms, due to trauma, tear film dysfunction or palpebral abnormalities, etc.

Usually its installation occurs 1 to 2 days after contact, characterized by rapid appearance of clinical signs such as palpebral edema, hyperemia, mucopurulent secretion, membranes and / or pseudomembranes.

The main infectious agents in adults are *H. influenzae*, staphylococci and streptococci. *H. influenzae*, *S pneumoniae*, and *Moraxella catarrhalis* are the most frequent agents in children. The course of the clinical picture is 7 to 10 days long.

Due to its clinical presentation, it is convenient to divide them according to their installation time, in acute, acute or chronic hyperinflation, and can guide diagnostic tests and empirical treatment according to the time of presentation.

Common pathogens according to the time of evolution

Acute	Híper Acute	Chronic
Staphilococcus Aureus.	Neisseria Gonorreae.	Moraxella catarrhalis.
Streptococcus pneumoniae.	Neisseria meningitidis.	Moraxella Lacunata.
Haemophilus influenzae.		Enterobacterias.

Special conditions:

In sexually active subjects who do not give up the clinical picture with empirical treatment (ceftriaxone 1gr b.i.d), we should investigate *Chlamydia Trachomatis* and add the relevant treatment.

In the case of infants or minors (less than 2 years old), we should consider granting systemic treatment because 50% of them concur with infections in other systems.

In oculo-vaginal infections we must investigate on strains compatible with trachoma (A-C); since we must remember that it affects more than 40 million subjects in areas of poor hygiene and continues to be a leading cause in non-reversible blindness.

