In other regions, such as India (with characteristics probably similar to our environment) it is observed that *S. Aureus* frequently causes infections of the eyelids and conjunctiva, *S. pneumoniae* is responsible for those inherent to the lacrimal apparatus and *S. coagulase negative* corresponds to infections intraocular.

In 10-year reviews in developed countries (eastern US) 1997- 2008, a tendency is observed in turn to the prevalence of *Staphylococcus Aureus* as the main ocular pathogen.

The effectiveness of 4th generation quinolones in the treatment of bacterial conjunctivitis since 1 year of age with a posology that varies from 2 to 4 times a day has been demonstrated in recent evidence, which corresponds to the preclinical studies and phase I of the drug. viii

We can also state the following points that support its use in infants and children under 18 years.

Due to the satisfactory results of the phase I study of the medication carried out in the adult population, in a phase II its implementation is justified in the child population since the evidence collected in said study allows inferring that its use is safe and effective to use it in the model of proposed disease, bacterial conjunctivitis. ix

Also the incidence of adverse events of musculoskeletal toxicity in children with chronic use of quinolones of 4th generation is reported as not significant at 5-year follow-up, so it was concluded that its use is adequate in this population. viii, ix

Currently, up to 26% resistance to the 4th generation quinolones (moxifloxacin, gatifloxacin and levofloxacin) is reported in strains of methicillin-resistant *Staphylococcus epidermidis*, so pazufloxacin represents a treatment option in such cases. ix, x

Sophia S.A de C.V. has developed a new ocular topical formulation belonging to the group of the fourth-generation quinolones, called Pazufloxacin mesylate, which has shown through in vivo and in vitro studies to have greater antimicrobial activity against methicillin-resistant *S. aureus*, *Haemophilus influenzae* ampicillin resistant, as well as *E. coli*, *Proteus mirabilis*, *Serratia marcescens* and *P. aeruginosa*. It should be noted that this formulation is free of preservatives.

Initially indicated for all those patients with bacterial conjunctivitis to susceptible organisms.

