16.3 Previous and concomitant treatments

Prohibited treatments

Table 4 shows the list of prohibited treatments during the study.

If a prohibited treatment is absolutely necessary during the study, the subject should be removed from the study.

Table 4. Main prohibited treatments (during the study)

Medicamento		Vía de administración
Grupo	Prototipo	
Betalactámicos	Penicilinas, Cefalosporinas, Monobactams, Carbapenems.	Tópica
Aminoglucósidos	Gentamicina	Tópica
Azúcares complejos	Clindamicina	Sistémicas
Polipeptídicos	Polimixina	Tópica
Rifamicinas	Rifampicina	Sistémica
Tetraciclinas	Clortetraciclina	Tópica
Amfenicoles	Cloramfenicol	Tópica
Macrólidos	Eritromicina	Sistémico
Miscláneos	Espectinomicina, Virginiamicina, Vancomicina, Teicoplanina, Capreomicina, Cicloserina, Fosfomicina, Novobiocina, Linezolida	Tópica, Sistémico
Quimioterapicos antibacterianos	Sulfonamidas Sulfonamidas + Trimetoprim Nitrofuranos Derivados de Naftiridinay Quinolonas	Tópica, Sistémico
Antiinflamatorios no esteroideos	Ketorolaco. Diclofenaco, nepafenaco, meloxicam,	Tópica
Esteroides	Prednisolona, dexametasona, triamcinolona, fluorometolona, loteprednol.	Tópica, Sistémico
Lagrimas artificiales con conservador		Tópica
Antihistamínicos	Epinastina	Tópica
Descongestionantes	Nafazolina , Oximetazolina, etc	Tópica
Estabilizadores de mastocitos	Cromoglicato de Sodio, etc	Tópica
Quinolonas 3era o 4ta generación	Moxifloxaciono. Gatifloxacino	Tópica
Quinolonas 2da, 3era o 4ta	Ciprofloxacino, Levofloxacino, Ofloxacino.	Sistémicas.

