16.5 Compliance with treatment

- With the accounting of the study medication returned.

- Patients will have a "diary of the subject" where they will have to write down the time of application of the drop and any incident or setback at the time of the application of the drop, for example, forgetfulness in the application of the drop, application of extra drops, etc.

- The adherence to treatment must be greater than 80%

After the discontinuation of the study treatment, the subject will return with the previously used treatment.

17. Methods and times of measurements.Scales to fill out by the researcher:

A meeting of researchers will be organized for all those involved in carrying out the study before starting it, and their participation will be mandatory. The objective of these sessions is to train them on the assessment of the efficacy and safety criteria and to ensure reliability among the qualifiers. In addition, detailed qualification rules will be provided to the qualifiers

The scales should always be evaluated by the same evaluating physician, either the principal investigator or an ophthalmologist previously designated in the Delegation of Responsibility format throughout the study, at the beginning of each visit. A guide will be made available for the interview to be carried out in each of the visits.

Self-qualification questionnaires to be completed by the patient:

Initials of the subject	
-------------------------	--

Mark with an X in any of the following options with which you have identified more in the course of the clinical study.

DEGREE OF SATISFACTION OF THE SUBJECT	ANSWER
Very bad: Intense and unbearable nuisances.	
Mal: Moderate intensity, intermittent, not tolerable.	
Regular: Discomfort of moderate intensity, intermittent and tolerable.	
Good: Mild and occasional nuisances.	
Very good: No discomfort (absent).	

The researcher will apply to the subject a questionnaire that he / she will have to answer at the end of the study where the satisfaction is evaluated upon finishing his / her participation in the study.

Visual acuity

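### Section 15.2 lets a patient still infected after moxifloxacin or gatifloxacin be randomised to that same drug, which can tilt the non-inferiority comparison toward PRO-157

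*Combined protocol and SAP*

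**What the plan says.** Exclusion 5 in section 15.2 removes patients on any antibiotic on the day of the baseline visit. Later in the same section, on previous and concomitant treatment, the protocol states: "If the patients prior to this day were under treatment with another antibiotic or drugs of those mentioned may be included". No drug is excepted, no interval is set, and there is no rule on earlier treatment failure.

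Section 15.2 sends the reader to Table 4 for rest periods. The table's title is "Table 4. Main prohibited treatments (during the study" (the bracket closes there). Its columns are group, prototype and route. One row covers topical third- or fourth-generation quinolones, with the prototypes "Moxifloxaciono. Gatifloxacino". No rest period is shown.

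The hypothesis in section 6.1 is non-inferiority to moxifloxacin and gatifloxacin. Section 16.1 lists five arms, none of them vehicle. Section 5 reports one human study of PRO-157, in healthy volunteers, and exclusion 9 bars trial participation in the last 40 days.

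The protocol allows for earlier medication in general terms. Section 16.5 says: "After the discontinuation of the study treatment, the subject will return with the previously used treatment". The elimination criteria say: "you will be prescribed again the medication of which you were already a user", and go on to allow any other beneficial drug instead.

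**The concern.** A patient with active conjunctivitis after a course of moxifloxacin is, on average, a poor responder to moxifloxacin. The plan lets that patient be randomised to moxifloxacin again. No patient can enter as a poor responder to PRO-157. Randomisation balances how many such patients each arm receives, but not how well each drug works in them.

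In a non-inferiority trial without a vehicle arm, a lowered comparator rate makes the favourable conclusion easier to reach, and the trial has no internal standard that would show it had happened. The sponsor's own rationale makes the direction plausible. Section 4.1 (Justification) cites "up to 26% resistance to the 4th generation quinolones (moxifloxacin, gatifloxacin and levofloxacin") in methicillin-resistant *S. epidermidis* and presents pazufloxacin as an option for such cases, which implies incomplete cross-resistance, at least in those strains.

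**Working it through.** **The plan's own figures.** The Fleiss formula in Annex 1 gives 147.2 per group for 69.8% against 53.3% (stated: 147; rounding up gives 148) and 43.7 for 92.34% against 66.12% (stated: 44). Both reproduce. They compare drug with placebo and do not depend on the entry rule.

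**Inputs from section 23 and the synopsis.** Drug rate C and vehicle rate V: 92.34% and 66.12% (specific eradication), or 69.8% and 53.3% (absolute eradication). 60 eyes per arm.

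**Assumptions, because the documents are silent.**
- Margin of 10 points, with PRO-157 truly 10 points worse in all other eyes: T = C − 0.10.
- A share g of eyes, equal in both arms, has already failed that arm's comparator. In these eyes the comparator clears at the vehicle rate V.
- In these eyes PRO-157 clears at V (full cross-resistance) or at T (none).
- Eyes are independent, and every eye counts in the analysis.

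**Formulas.**
- Comparator arm: pc = (1−g)C + gV
- PRO-157 arm: pt = (1−g)T + gx, with x = V or x = T
- SE = √{[pc(1−pc) + pt(1−pt)]/60}
- False non-inferiority = 1 − Φ(1.96 − [0.10 − (pc − pt)]/SE)

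**Example:** first rates, g = 20%, no cross-resistance. pc = 0.8×0.9234 + 0.2×0.6612 = 0.8710. pt = 0.8234. Measured deficit = 4.76 points. SE = √[(0.8710×0.1290 + 0.8234×0.1766)/60] = 0.0655. (0.10 − 0.0476)/0.0655 = 0.80, and 1 − Φ(1.96 − 0.80) = 12.3%.

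| Rates | g | Comparator arm | Measured deficit, full → no cross-resistance | False non-inferiority, full → none |
|---|---|---|---|---|
| 92.34/66.12 | 5% | 91.0% | 9.5 → 8.7 | 3.0 → 4.0% |
| | 10% | 89.7% | 9.0 → 7.4 | 3.6 → 6.1% |
| | 20% | 87.1% | 8.0 → 4.8 | 4.8 → 12.3% |
| 69.8/53.3 | 5% | 69.0% | 9.5 → 9.2 | 2.9 → 3.1% |
| | 10% | 68.2% | 9.0 → 8.4 | 3.2 → 3.8% |
| | 20% | 66.5% | 8.0 → 6.7 | 4.2 → 5.7% |

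At g = 0 every entry is 2.5%. With a 15- or 20-point margin (true deficit set equal to the margin) and g = 20%, the range over both rate pairs is 5.2 to 11.5%.

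**Separating selection from dilution.** At the full cross-resistance end both drugs clear at V in the affected eyes, so a 10-point deficit shrinks to 10(1−g). That is dilution by non-responders, not selection against one drug. A second model isolates the selection: PRO-157 keeps its whole deficit and shares a fraction c of the comparator's loss. The shift toward PRO-157 is then g(1−c)(C−V).
- c = 0 and g = 5, 10, 20%: 1.3, 2.6 and 5.2 points (first rates), or 0.8, 1.7 and 3.3 points (second rates).
- c = 0.5: half of that. At g = 20% and a 10-point margin, false non-inferiority is 5.8% or 3.8%.
- c = 1: no shift, and false non-inferiority stays at 2.5%.

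**The case against.** A reader might infer that the rule weakens the comparators alone. The documents do not support that. Section 4.1 (Justification) places pazufloxacin in the same fourth-generation quinolone class, so organisms that survived a comparator may also respond less to PRO-157. The remark about resistant strains concerns methicillin-resistant *S. epidermidis* only. Elsewhere in that section the sponsor claims equal effectiveness. The bias is conditional on incomplete cross-resistance.

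A reader might also infer that comparator failures will be common. No section shows this. The introduction says "35% refer to ophthalmologists because it is a case that does not remit with symptomatic or because the severity warrants it", but this describes failed symptomatic care or severity in conjunctivitis generally, not failed antibiotics. The sentences on returning to earlier medication are generic and name no antibiotic. Together they make prior use possible and give no frequency.

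The rates are published eradication rates. Section 7.1 counts a drug as effective on clinical or microbiological remission, a more lenient composite for which no effect has been estimated. The 12.3% combines g = 20%, no cross-resistance, the higher rate pair and an assumed margin. If 20% of eyes had used either comparator and use split evenly, g would be at most 10%, and the ceiling would be 6.1% (first rates) or 3.8% (second).

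These limits on size stand. Two defences of the text do not. Exclusion 6, on medication that would decisively affect the results, is discretionary, has no window and sits beside an express permission. The pointer to Table 4 for rest periods leads to none. Even if the permission is read as covering only antibiotics other than the study drugs, no criterion excludes earlier comparator use.

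**Conclusion.** The point holds as a conditional bias. The entry rule admits patients who remain infected after a comparator and allows them to be randomised to it again. No counterpart exists for PRO-157. The comparison can move toward non-inferiority to the extent that cross-resistance is incomplete; with full cross-resistance only dilution remains.

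Under the stated assumptions the effect is small at g = 5% and becomes material at g = 20% only when cross-resistance is low and the higher rate pair applies. The margin, g and the degree of cross-resistance are all absent from the documents, so these are illustrations and not estimates. Nothing is claimed about earlier use of other antibiotics, where the direction is unknown. This is a cheap improvement, not evidence that the trial would mislead.

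**What to change.** Add one exclusion criterion to section 15.2: topical moxifloxacin or gatifloxacin in either eye for the current episode, or in the 10 days before baseline. The episode clause catches failures more than 10 days old. Ten days is the upper end of the protocol's own illness course ("The course of the clinical picture is 7 to 10 days long"), used as a practical limit and not as a pharmacological washout. Enter the same rest period in the comparator row of Table 4. Users of other antibiotics stay eligible, with drug and last-dose date recorded at baseline.

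The arms stay at 60 eyes, so precision is unchanged. The cost is slightly slower recruitment and a somewhat narrower population. Let u be the share of otherwise eligible eyes that had used either comparator (this is not g, which counts failures on one drug). The eyes to find are 300/(1−u): 316, 334 or 375 at u = 5, 10 or 20%. Over the planned 4 months that is 79, 84 or 94 per month instead of 75. If failures on the two drugs are separate and 20% had failed each, u is at least 40% and the figure is 300/0.6 = 500.

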15.1 Inclusion Criteria

All selected subjects:

- They will have an age between 0 to 99 years * see note.
- They will be obtained in the external consultation.
- With diagnosis of bacterial conjunctivitis (signs and / or symptoms and / or culture)
- Signed and dated Informed Consent (Informed Consent and parental consent in case of being a minor)

* NOTE: In the case of inclusion of subjects from 0 years to less 18 years minus 1 day, they will be included progressively as follows:

- Age group of 12 to 18 years.
- Age group from 2 to 12 years old.
- Age group from 0 to 2 years.

This with the intention of integrating patients once the dosage parameters have been established as safe and recommended for the younger age groups.

The indications of the inclusion periods will be made as the results are gathered in the groups of minors.

The Informed Assent will only apply to minors who demonstrate understanding of the study, at the discretion of the researcher.

- Physical examination of patients

In the examination carried out during the baseline visit, a general and ophthalmological clinical history will be performed, initially including and starting treatment with all those patients clinically suspected of bacterial conjunctivitis. If the culture is negative but clinically there is improvement, you can continue with the treatment until the last day of the stipulated study. At the baseline visit a urine pregnancy test will be performed (if applicable).

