18.2 Times of Measurements

Clinical examination

Basal visit (Day 1)

The principal investigator or the head of the research team of the site duly specified must obtain the letter of informed consent of each of the subjects, before carrying out any procedure of the study.

When the informed consent is obtained and all the inclusion criteria and none of exclusion are met, a unique identification number of the subject will be assigned, this will be used throughout the study for its identification.

Female subjects who are of reproductive age will be tested for pregnancy in urine.

The following evaluations will be made:

Signature of informed consent

Review of inclusion criteria and exclusion criteria,

Demographics,

Urine pregnancy test (if applicable),

General and ophthalmological clinical history,

Clinical Photography,

Sampling of conjunctival sac fundus for culture,

Assigning number to the subject,

Delivery of medication,

Ocular symptoms: burning, tearing, foreign body sensation, pruritus, photophobia

Visual acuity and / or visual ability,

Anterior biomicroscopy: Conjunctival hyperemia, chemosis, secretion, palpebral edema, membranes and / or pseudomembranes, scales, epitheliopathy,

Fluorescein staining,

Green stain of lysine,
Posterior segment revision: Retina, Macula, Vitreous and Optic nerve.
Evaluation of adverse events.

This day the patient will be included, if clinically it suggests a bacterial conjunctivitis, it will be randomized and at that same moment a clinical photograph of his eyes will be made and a sample will be taken for culture of both eyes, immediately he will go with the person previously designated to randomize him, this person will not be masked and will give specific instructions to the patient on how to apply the study medication and will remember the importance of the patient not mentioning the study's evaluating physician how many times the treatment is applied, then he will start with the study medication regardless of the crop results.

Treatment visits:**Visit 1 (Day 3)**

Between the days of study there may be a window of \pm 1 day. If for any reason an assessment is made on any day not planned in the study, this information should be recorded in the unscheduled visit format found within the FRC.

At each follow-up visit, an ophthalmological examination will be performed in order to evaluate the following parameters.

1. Acuity and / or Visual Ability
2. Clinical Photography,

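### Entry admits bacterial conjunctivitis of any onset class, but elimination lists any diagnosis other than acute disease, so eligible randomised patients can be lost from the arm comparison

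*Combined protocol and SAP*

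**What the plan says.** **Entry.** Section 15.1 asks for patients "With diagnosis of bacterial conjunctivitis (signs and / or symptoms and / or culture". It does not use the word acute and sets no time since onset. The same section describes "initially including and starting treatment with all those patients clinically suspected of bacterial conjunctivitis". Section 18.2 fixes the moment of allocation: "This day the patient will be included, if clinically it suggests a bacterial conjunctivitis, it will be randomized". Treatment then starts whatever the culture later shows. The title, the objectives, the summary and section 8 also speak of bacterial conjunctivitis without qualification.

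**Exclusion.** The only types of conjunctivitis excluded by the ophthalmological criteria in section 15.2 are given as "Suspected viral or allergic conjunctivitis". Chronic and hyperacute bacterial disease are not named.

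**Elimination.** Further on in section 15.2, the clinical elimination criteria open with "Any complication or lack of control that the doctor considers should be treated differently. The following points should be considered". The second point beneath is "Diagnosis added or different to that of acute bacterial conjunctivitis".

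**Disease classes.** The introduction in section 4.1 says of bacterial conjunctivitis that "it is convenient to divide them according to their installation time". It then tabulates acute, hyperacute and chronic forms with different pathogens.

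**Analysis.** Section 15.3 retains the available data of prematurely withdrawn patients for the safety analysis and labels that set ITT. In section 23 (Analyzed data set), the ITT population is every recruited subject with at least one dose and is used to describe each variable. The bivariate analysis is done in the per-protocol subset, meaning those without a major deviation. A major deviation is not defined.

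**The concern.** Entry and elimination use different disease definitions. The wider one decides who is randomised. The narrower one can be applied afterwards, by a doctor who is also asked to weigh lack of improvement in the same list. Onset class could usually be established from the history taken at baseline. Here it defines no entry limit, yet it becomes a possible ground for removal once treatment has begun.

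What is at stake is the set of patients in which the arms are compared. The hypothesis is non-inferiority of PRO-157 to two active comparators. If patients who met every entry criterion leave after randomisation, and only a per-protocol set is compared, the comparison no longer rests fully on the randomised groups.

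**Working it through.** The plan gives no figure on this point, so the check is mainly a comparison of the sections.

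1. **Can a chronic or hyperacute bacterial case enter?** Section 15.1 requires a diagnosis of bacterial conjunctivitis, and section 18.2 requires a clinical picture suggesting it. Neither sets an onset limit. The exclusions name only viral and allergic forms. General exclusion 11 (clinically important abnormalities that could interfere) could be stretched to such a case, but it mentions neither onset nor duration. So the answer is yes.

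2. **Does that patient then meet a listed elimination point?** Section 4.1 makes acute one of three classes, so on the protocol's own terms a chronic or hyperacute case is a diagnosis different from acute bacterial conjunctivitis. The answer is yes, as a matter for the doctor to consider and not as automatic removal.

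3. **What happens to the patient's data?** A removed patient who took one dose is in the ITT population by definition, but that population is only described. Section 15.3 promises the data for safety and says nothing about efficacy. Section 23 does not say whether elimination is a major deviation, or whether the patient counts as a failure, as missing or as excluded. If elimination is treated as a major deviation, the patient leaves the only arm comparison planned.

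4. **How many?** The documents give no share of chronic or hyperacute cases and no dropout allowance. As an assumption only, take a removed share r of each group of 60 eyes, leaving 60 × (1 − r):
   - r = 5%: 60 × 0.95 = 57
   - r = 15%: 60 × 0.85 = 51
   - r = 30%: 60 × 0.70 = 42

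   The smaller of the two sample sizes in Annex 1 is 44 per group. It reproduces as 44 from 92.34% against 66.12% with the continuity-corrected Fleiss formula. A group would fall below it once r exceeds 1 − 44/60 = 26.7%. That calculation compares drug with placebo, so 44 is only a reference point here and not the requirement for non-inferiority. The contradiction does not depend on r.

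**The case against.** The strongest reply is that this is one loose word. The elimination text is a prompt for problem cases, and an added or different diagnosis may simply mean one that emerges after entry. The title, objectives and section 15.1 all agree with each other. This stands in part: such cases are removable, not removed by rule. But section 4.1 uses acute as a defined class, so the mismatch cannot be dismissed as style.

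A second reply is that a baseline feature is balanced across arms in expectation and that the evaluator is masked (sections 8 and 16.2). This also stands against any claim that bias has been shown. It does not make a discretionary decision, taken after the patient's course is known, harmless.

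A reader might infer three stronger points that the documents do not support.

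- **That about 10 of 60 eyes per arm would be removable.** The isolate counts in section 4.1 (Justification) give 80/0.237 ≈ 338 isolates. Those from the hyperacute or chronic columns, counting *E. coli* and *Klebsiella* as enterobacteria, are 13 + 10 + 15 + 18 = 56, or 16.6%. This equates organism with clinical form. Only 66.7% of the isolates were conjunctival, *M. catarrhalis* is also listed as frequent in children, and the elimination point concerns diagnosis, not organism. *N. gonorrhoeae* alone is 13/338 = 3.8%. None of these is a removal rate.
- **That culture results would trigger removal.** Section 17 asks the laboratory to look for these organisms, treatment starts regardless of culture, and section 15.1 lets improving culture-negative patients continue.
- **That an onset limit is needed.** Section 4.1 states "The course of the clinical picture is 7 to 10 days long", and the final visit falls 7 days after baseline. A patient entering 3 days after onset finishes at 3 + 7 = day 10. At the lower bound of 7 days, even a patient entering on the day of onset has run the natural course. A 3-day limit would not solve this, and it could turn away many patients from an ophthalmology clinic.

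**Conclusion.** The inconsistency is real and rests on the text alone. A bacterial case of any onset class is eligible, and a non-acute one then meets a listed, discretionary ground for elimination. It matters because the only planned arm comparison is per protocol, with no definition of a major deviation and no commitment to keep removed patients' efficacy data.

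The size is unknown. The 5% to 30% range in the working is an assumption, not an estimate. Removal that differs by arm is possible but not demonstrated. The conclusion assumes that the word acute carries the meaning section 4.1 gives it, and that an eliminated patient could be classed as a major deviation, which the plan neither states nor rules out. It is a moderate point with a cheap remedy.

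**What to change.** 1. Reconcile the inclusion, exclusion and elimination wording in sections 15.1 and 15.2 with the title and objectives, so that one disease definition governs both entry and elimination. Whether to restrict the trial to acute disease, or to set an onset limit, is for the sponsor to decide.
2. In section 23, add an ITT arm comparison reported alongside the per-protocol one. State that a randomised, treated patient who met the entry criteria stays in it even if the onset class or diagnosis is revised later. Say how that patient's efficacy outcome is counted, and define a major deviation.
3. Record the onset date on the FRC from the history already taken at baseline, so that results can be described by onset class.

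The cost is an amendment of wording, one FRC field and a little more analysis. The ITT comparison will include some patients whose diagnosis was revised, which is why the per-protocol result should stand beside it.
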